## 11.0 Assessment of Radiologic Response

### 11.1 Imaging Acquisition

Participating centers will need to comply with minimum technical requirements for CT and MR as shown in Tables 5 and 6.

#### 11.1.1 Importance of High-Quality, Carefully Timed Multiphasic Contrast-Enhanced Imaging

It is well known in the imaging community that optimal detection of liver nodules with predominant arterial vascular supply (such as HCC) on cross-sectional imaging (CT or MRI) requires careful timing of image acquisition to take place during late arterial phase of contrast enhancement. At that point in time there is maximal signal-to background contrast between capillary enhancement in the lesion and surrounding hepatic parenchyma. In most patients, early arterial phase imaging does not improve tumor conspicuity by either quantitative or subjective analysis.

There is a relatively small time window for acquisition of the late arterial phase, which persists for approximately 10 seconds in most patients and explains the need for careful timing.

While also important for diagnostic purposes, the time window of opportunity to acquire images of the hepatic parenchyma during portal vein and equilibrium (delayed) phase is much wider. Therefore it is permissible to use fixed-time delays (approximately 60 to 75 seconds post injection preferred) of the liver which must be obtained in a single breath hold helical acquisition. HCC has a range of presentations on CT. The most diagnostic images are the properly timed multi-phase contrast-enhanced images. The following section covers the key elements necessary to achieve optimal diagnostic sensitivity and specificity, as well as an optional pre-contrast imaging sequence recommended especially after ablative therapy.

## 11.1.2 Guidelines for Multiphasic Contrast-Enhanced CT Imaging

### 11.1.2.1 Pre-contrast: Recommended but not required

Non-contrast imaging through the liver prior to contrast-enhanced imaging is optional and not required for the purpose of this protocol.

### 11.1.2.2 Late arterial phase

Imaging characteristics include the following:

- Fully enhanced hepatic artery and branches;
- Early contrast enhancement of portal vein;
- Lack of enhancement of the hepatic venous system.

Time to peak enhancement in abdominal aorta at celiac axis level can be determined either by timing bolus injection or through the use of triggering facility provided on newer scanners. Some scanners have an auto triggering feature that commences the scan when a pre-defined threshold (typically 100 HU) is reached in the target area; some scanners will display a time-density curve at the pre-defined anatomic location to the technologist and require a manual start of the exam. Either mechanism optimizes timing of the scan to the cardiac output and circulatory time of the individual participant and is strongly preferred over a fixed-time delay exam. Late arterial phase scanning should typically commence 5 to 10 seconds after peak enhancement in the upper abdominal aorta at the level of the celiac axis. In the unlikely event that fixed time delay needs to be used, an empirical delay of 25 to 30 seconds may work for most participants.

### 11.1.2.3 Portal vein phase

Imaging characteristics include the following:

- Fully enhanced portal vein;
- Peak liver parenchymal enhancement;
- Early contrast enhancement of hepatic veins.

The time window of opportunity to acquire images of the hepatic parenchyma during portal vein and equilibrium (delayed) phase is relatively wide. Portal vein phase images should typically be acquired 35 to 55 seconds after initiation of late arterial phase.

### 11.1.2.4 Equilibrium/Delayed phase

Imaging characteristics include the following:

- Variable appearance;
- >120 to <180 seconds after initial injection of contrast.

The time window of opportunity to acquire images of the hepatic parenchyma during portal vein and equilibrium (delayed) phase is relatively wide. Equilibrium phase images should typically be acquired 120 to 180 seconds post initial contrast injection.

**Table 5: Minimum technical specifications for multiphasic contrast-enhanced CT of the liver**

Feature	Specification	Comment
Scanner type	Multidetector row scanner	
Detector type	Minimum of 8 detector rows	Need to be able to image entire liver

		during brief late arterial phase time window
Reconstructed slice thickness	Maximum of 5 mm reconstructed slice thickness	Thinner slices are preferable, especially if multiplanar reconstructions are performed
Injector	Power injector, preferably dual chamber injector with saline flush	Bolus tracking desirable
Dynamic phases on contrast enhanced MDCT (comments describe typical hallmark image features)	
0) OPTIONAL: Pre-contrast
 <hr/> 
1) MANDATORY: Late arterial phase
 <hr/> 
2) MANDATORY: Portal venous phase
 <hr/> 
3) MANDATORY: Equilibrium/Delayed phase
	
1) Artery fully enhanced, beginning contrast enhancement of portal vein
 
2) Portal vein enhanced, peak liver parenchymal enhancement, beginning contrast enhancement of hepatic veins
 
3) Variable appearance, >120 sec after initial injection of contrast

Dynamic phases (timing)	Bolus tracking preferred over timing bolus for accurate timing	

### 11.1.3 MR Imaging

#### 11.1.3.1 General MRI parameters are outlined in the table and text below.

- Field strength of 1.5 Tesla or greater.
- Imaging must be performed with a specialized torso array coil or other local coil combinations appropriate for body imaging. Body coil for signal reception is not acceptable.
- Image slice thickness should be  $\leq 10$  mm.
- Field of view (FOV) as appropriate for given patient body habitus.
- Matrix for T1 and T2 weighted images should be no less than 256 (frequency) x 128 (phase).
- Diffusion-weighted imaging may be used by sites per institutional protocol but is not required by this trial protocol. If sites perform this type of imaging, the use of lower resolution matrices is acceptable.
- For axial imaging, phase encoding should be anterior–posterior.
- For contrast-enhanced scanning, standard extracellular gadolinium chelates that do not have dominant hepatobiliary excretion should be used at a dose of 0.1 mmol/kg to a maximum of 20 mL.
- Injection rate should be 2 cc/sec, and all injections must be followed by a saline flush of 30 cc. Peripheral IV access is preferred.

#### 11.1.3.2 Abdominal MRI

Contrast-enhanced imaging with a standard extracellular gadolinium chelate that does not have dominant hepatobiliary excretion is required for MRI. Scanning protocol should be per institutional standards, but should include at a minimum: pre-contrast (mandatory) and dynamic post-extracellular-gadolinium T1-weighted (T1W) gradient echo sequence (3D preferable), T2W (with and without FAT

SAT), T1W in and out of phase imaging. The inclusion of other imaging techniques/planes is acceptable per institutional/imaging center's standard.

#### 11.1.3.3 Guidelines for Multiphasic Contrast-Enhanced MR Imaging

HCC has a range of presentations on MRI. The most common is a circumscribed mass that may be inconspicuous on pre-contrast T2W and T1W imaging. The strongest diagnostic images are the multiple contrast-enhanced timed T1W images. The key elements necessary to achieve optimal diagnostic sensitivity and specificity are the following:

- 3D Gradient Echo (GRE) fat-suppressed acquisitions acquired with identical parameters throughout the pre- and post-contrast series. 3D volumetric imaging is preferred, but multiplanar 2D imaging is acceptable.
- Pre-contrast T1W images:
  - 2D or 3D in- and opposed-GRE;
  - 3D GRE (depending on scanner platform used: Vibe; Lava-xv; Thrive) with fat suppression.
  - Parameters identical to the post-contrast 3D GRE sequence:
  - Avoid misinterpreting a nodule intrinsically with high T1W signal as an enhancing mass, as can be seen in regenerating nodules or dysplasia. Comparison must always be made between the pre-contrast and arterial phase images. Use of subtraction images is strongly recommended.
  - Examine the in/out-of-phase images for fat. Occasionally the T1 signal may be lower than adjacent liver on fat-suppressed 3D GRE due to lipid, < 10% incidence.

##### 11.1.3.3.1 Pre-contrast: Mandatory

Non-contrast imaging through the liver prior to contrast-enhanced imaging is mandatory.

##### 11.1.3.3.2 Arterial phase

- Imaging characteristics include the following:
  - Fully enhanced hepatic artery and branches;
  - Early contrast enhancement of portal vein;
  - Lack of enhancement of the hepatic venous system.
- Acquisition of a properly timed late arterial phase is the most technically challenging and diagnostically critical element of the dynamic liver examination.
- Using set (empirical) timing delays from the start of the injection will be associated with a large range of contrast arrival times (from < 12 to > 30 seconds range timed from the start of the contrast injection to the arrival in the hepatic artery) and will not provide the most optimized method.
- HCC will transiently enhance over a period of 5 to 10 seconds above the adjacent liver parenchyma signal, therefore the timing is critical and is optimized if:
  - The gadolinium bolus is injected in as short a time as possible;
  - Peak HCC enhancement must be aligned in time with the time during the 3D GRE acquisition that accumulates low k-space frequencies (e.g., linear order = align at middle of breath hold; low to high ordering = align at beginning of breath hold, which means adding a longer delay time to account for this).
- The following is required for optimized timing in order to achieve an arterial-phase breath hold liver examination (ABLE):
  - Dual chamber power injector;

- Injection of contrast at 2 cc/sec (measured to the recommended dose by weight; standard extracellular gadolinium chelates that do not have dominant hepatobiliary excretion should be used at a dose of 0.1 mmol/kg to a maximum of 20 mL);
- Chase with saline at 2 to 3 cc/sec x 30 cc;
- Start a real-time reconstruction high-speed, low-quality coronal (suggested) GRE (e.g., care-bolus) at the start of the infusion for bolus monitoring;
- Field of view on coronal set to allow visualization of the heart, mediastinum, and centered on the diaphragm to visualize the celiac axis;
- Technologist trained to recognize filling of the right side of heart, pulmonary artery, left heart, aorta, in preparation for recognizing bolus arrival;
- Stop the bolus imaging and start timing when the contrast arrives at the celiac axis (diaphragm);
- Count 8 sec if using a linear ordered 16 to 18 sec breath hold acquisition time 3D GRE (based on data looking at perfusion kinetics of arterial enhancing tumors);
- During this time give the breathing commands and train the technologists to provide adequate time for the participant to complete the breath hold maneuver 2 to 3 sec prior to initiation of the sequence to allow the participant to complete following the command and stop all voluntary movements;
- Start the arterial phase acquisition.
- An approximate guide to show that an ideal acquisition was obtained usually shows the hepatic artery fully enhanced and the portal veins centrally just enhancing to well enhanced; hepatic veins show no enhancement.

#### 11.1.3.3.3 Portal venous phase (AKA venous and blood pool phase)

- Imaging characteristics include the following:
  - Fully enhanced portal vein;
  - Peak liver parenchymal enhancement;
  - Early contrast enhancement of hepatic veins.
- Images captured just after the hepatic veins have filled with contrast. Timing is less critical and can be acquired (35 to 55 sec after initiation of late arterial phase scan). Typically the portal venous phase is started one or two breathing cycles after completion of late arterial phase.
- This provides adequate time for the participant to regain their breath before being asked to perform the next breath hold and reduce motion effects from poor breath holding due to rushing this second enhanced acquisition.
- This acquisition provides optimal visualization for portal or superior mesenteric vein (SMV) thrombosis and varices.

#### 11.1.3.3.4 Equilibrium phase (AKA extracellular, interstitial, or delayed phase)

- Imaging characteristics include the following:
  - Variable appearance;
  - >120 to <180 seconds after initial injection of contrast.
- Timing less critical and can be acquired at 120 to 180 sec post injection as a third breath hold. This provides adequate time to visualize HCC —wash-out.
- The signal in the HCC is lower in this phase due to a combination of lower vascular volume and interstitial uptake than in the adjacent liver.
- The margins of the HCC enhance, forming an apparent thin pseudocapsule.

**Table 6: Technical specifications for multiphase contrast-enhanced MRI of the liver**

Feature	Specification	Comment
Scanner type	1.5 T or greater magnetic field strength	Low-field magnets not suitable
Coil type	Phased-array multichannel torso coil	Unless patient-related factors preclude use (e.g., body habitus)
Gradient type	Current generation high speed gradients (providing sufficient coverage)	
Slice thickness	5 mm or less for dynamic series; 8 mm or less for other imaging	
Injector	Dual chamber power injector recommended	Bolus tracking desirable
Contrast injection rate	2–3 mL/sec of extracellular gadolinium chelate that does not have dominant hepatobiliary excretion	Preferably resulting in vendor recommended total dose
Required non-dynamic sequences	T1W in and out of phase imaging T2W (per institutional standard, not STIR)	Optional diffusion imaging
Dynamic phases on contrast-enhanced MRI (comments describe typical hallmark imaging features)	
0) MANDATORY: Pre-contrast T1W
 
1) MANDATORY: Late arterial phase
 
2) MANDATORY: Portal venous phase
 
3) MANDATORY: Equilibrium/delayed phase
	
0) Do not change scan parameters for post contrast imaging
 
1) Artery fully enhanced, beginning contrast enhancement of portal vein
 
2) Portal vein enhanced, peak liver parenchymal enhancement, beginning contrast enhancement of hepatic veins
 
3) Variable appearance, > 120 sec after initial injection of contrast

Dynamic phases (timing)	The use of a bolus tracking method for timing contrast arrival for late arterial phase imaging is preferable. Portal venous phase (35–55 sec after initiation of late arterial phase scan), equilibrium/delayed phase (120–180 sec after initial contrast injection)	
Breath holding	Max length of series requiring breath hold should be about 20 sec with a minimum matrix of 128 x 256	Compliance with breath hold instructions very important, technologists need to understand the importance of participant instruction before and during scan

#### 11.1.3.4 Serial imaging

Participants who are listed for liver transplant will undergo serial imaging scheduled in accordance with the 90-day intervals required for cyclical update of the HCC-exception points with UNOS. These images will be used to measure outcomes. For patients not on the transplant list, radiologic imaging will occur

four months ( $\pm$  4 weeks) after randomization and then every three months thereafter until the primary endpoint is met.

#### 11.1.4 Ablative Therapy and Post-ablation imaging

If multiple TACEs are planned, participants need to first complete the entire treatment scheme per institutional SOC before undergoing response assessment. In some participants, the post-ablation imaging time point may occur closer than 90 days to the next serial imaging time point required for liver transplant waitlist updates. Sets of post-ablation imaging studies that are less than 90 days old at the time of the next scheduled UNOS HCC-exception point update (serial) images do not have to (but may) be repeated at the time of exception point update and may count towards the serial imaging time point for the purpose of the trial. For the remainder of the trial, these participants continue to be imaged according to the OPTN/UNOS schedule for updating HCC-exception points. Should another round of ablative treatment become necessary, the above rules apply for all post-ablation imaging sets and subsequent serial time points.

Serial MR or CT imaging will be performed at distinct time points as dictated by OPTN/UNOS until transplantation. Timing of serial SOC imaging in waitlisted patients is dictated by OPTN/UNOS HCC-exception point update requirements (90 day intervals). Waitlisted patients are defined as those eligible for/scheduled to undergo LDALT as well as those waiting for livers from deceased donors to become available. Postablation imaging studies that are less than 90 days old at the time of the next scheduled UNOS HCC exception point update (serial) images do not have to (but may) be repeated at the time of exception point update and may count towards the serial imaging time point for the purpose of the trial.

**11.2 Local intrahepatic tumor:** The status of each treated tumor/target lesion will be assessed by MRI or CT scan and classified as progression if there is tumor growth (excluding growth due to biloma or abscess formation), residual or new enhancement of the ablated tumor (excluding benign peri-ablational enhancement), or contiguous viable tumor. Each treated intrahepatic lesion will be evaluated utilizing mRECIST Criteria for HCC (Appendix B). All imaging will be assessed at the treating institution. If concern for residual or progressive disease is raised, imaging will be reviewed a second time at the individual institutions' multi-disciplinary conference review.

If there is a discrepancy between the two interpretations, imaging will be de-identified (responsibility of the site sending) and transferred to Ambra, to be shared in a group. The panel of radiologists who will be providing the consensus opinion will access the images through Ambra. To accomplish this, the treating institution will pull the data out of PACS, de-identify the data using LB Compass (or similar software, depending on the institution preference) and then will visually inspect the data to confirm de-identification. Further tracking of the data will be done by the individual patients' assigned tracking number, by the treating institution. The treating institution will upload the data to Ambra for the radiology panel (only users internal /external that are pre-configured will have access). The treating site will add the assigned tracking number to a Google sheet that will track the pre and post PHI. The treating institution will email [name] (or designated individual) notifying that the data/images are available in Ambra for review. An email will then be sent to the panel of three independent radiologists so that a final radiologic consensus assessment can be made. The committee's judgment will be final. The treating institution will be notified of the result and the data will be uploaded to the EDS by the treating institution subsequently.

11.3 Disease-Specific Mortality: For this study, disease-specific mortality will be defined as death due to the subject's disease, or death due to treatment for the subject's disease. Time zero will be defined the day of the last treatment.

## **12.0 Criteria for Discontinuation of Protocol Treatment**

### **12.1 Off-Treatment Conditions**

- Unacceptable toxicity as defined in section 10.
- Therapy may be discontinued prematurely at any time by subject request without prejudice to subsequent care.
- Subjects may be removed from the treatment at any time per investigator discretion.

### **12.2 Off Study Conditions**

- Subjects will be removed if they are unable to receive either SBRT or TACE due to decompensation prior to initial therapy.
- Subjects may be removed from the study at any time by subject request.
- Subjects who go on to receive additional non-radiation therapy (i.e., treatment that is not TACE or SBRT related) will be followed for progression within the treated lesion(s). They will no longer receive protocol-directed treatment or testing.
- Subjects who develop extra-hepatic tumor will not be followed and will be censored from the data analysis.
- Subjects who undergo a liver transplant will be considered off study and will not be followed from that time point (except to determine 60-day post transplantation survival status).
- Subjects permanently removed from Liver Transplant list and will not be followed.

### **12.3 Adverse Event Guidelines**

#### **12.3.1 Adverse Event definitions**

- An Adverse Event is any untoward medical event that occurs in a subject who has received an investigational treatment, and does not necessarily have a causal relationship with the investigational treatment. An AE can therefore be any unfavorable and unintended sign (including abnormal laboratory finding), symptom, or disease temporally associated with the use of an investigational treatment, whether or not related to the treatment.
- Pre-existing diseases or symptoms or abnormal laboratory values present upon recruitment are not considered an AE even when observed during the further course of the study. However, every worsening of a pre-existing condition is considered an adverse event.
- All AEs  $\geq$  grade 3 will be collected and attributed either as possibly, probably or definitely related to protocol treatment or not related to protocol treatment. Additional AE's collected are, any grade  $\geq 2$  abdominal pain, nausea, vomiting, and fatigue. The NCI Common Terminology Criteria for Adverse Events Version 5.0 (CTCAE) will be utilized to grade AE's for AE reporting.

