### **10.1 Expected Toxicities after TACE:**

- Abdominal pain
- Nausea
- Vomiting
- Fatigue

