### **10.2 Expected Acute Toxicities after SBRT:**

- Fatigue
- Weight loss
- Nausea, vomiting, or anorexia.
- Abdominal discomfort.
- Skin irritation
- Increased frequency of bowel movements or change in stool consistency

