### **10.3 Possible long term toxicities after SBRT:**

- Gastric or Bowel injury (ulceration, bleeding, perforation, fistula formation, or obstruction)
- Biliary obstruction due to inflammation or sclerosis
- Liver abscess
- Hepatic subcapsular injury
- Decreased renal function.
- Rib fracture
- Myositis
- Radiation-induced liver disease (RILD) including potentially fatal liver injury.
- In subjects who have Grade 4 elevation of liver enzymes levels and/or in subjects with early nonspecific signs or symptoms of liver injury, close follow-up is recommended with repeat blood work. If no tumor progression is documented in these subjects, liver injury will be presumed to be treatment related.

Only grade  $\geq 2$  toxicities will be considered in the statistical analysis. The following toxicities will require subjects to be removed from protocol treatment if the protocol treatment has not yet been completed. Patients will be followed per physician standard of care.

- Grade  $\geq 4$  hepatic toxicity for changes in AST, ALT, alkaline phosphatase, or platelet counts attributed to treatment and not attributable to disease progression. Transient grade 4 (less than 10 days) hepatic toxicities are acceptable.
- Grade  $\geq 4$  Upper GI bleeding (**attributed to treatment**, and not attributable to disease progression).
- Death due to any cause.

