#### 17.2.3 Other Secondary Endpoints

Quantitative outcomes like number of retreatments and number of toxicities will be described by mean, standard deviations, median, minimum and maximum by treatment group and treatment group will be compared using a t-test. Categorical outcomes like any retreatment, any toxicity, radiologic response, pathologic response will be described by counts, percent and groups compared using the chi-square test. Overall survival, and 60 day post-transplant morbidity and mortality will be described by Kaplan-Meier estimates, and groups compared using the log-rank test and Cox model as for the primary outcome. Note, with 98 patients per arm, each arm will have 99% and 95% probabilities of observing at least one event of toxicity when the true probabilities per patient are 0.05 and 0.03. Further, when estimating proportion of patients to have a particular toxicity, the 95% confidence intervals will have precision of 10% or tighter, for each treatment group.

We will analyze secondary endpoints relating to time to event analogously to time to recurrence, and quantitative outcomes analogously to the analysis the HRQL endpoints.

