### **Safety Measures**

Lab measures will be described and groups compared as described using t-tests or Wilcoxon tests as appropriate.

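### As collected, the any-toxicity and number-of-toxicities comparisons count four symptoms from grade 2 and every other term from grade 3, and the plan does not say so

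*Combined protocol and SAP*

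**What the plan says.** All references are to the combined protocol and SAP.

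- **Collection (12.3.1).** Adverse events of grade 3 or higher are collected for every term. Grade 2 events are added for four symptoms only: "abdominal pain, nausea, vomiting, and fatigue".
- **Analysis floor (10.3).** Only grade 2 or higher "toxicities will be considered in the statistical analysis". No term is excluded.
- **Expected events.** The list headed "Expected Toxicities after TACE" (10.1) holds exactly those four symptoms. The acute SBRT list (10.2) has fatigue, nausea, vomiting and abdominal discomfort, and also weight loss, anorexia, skin irritation and "Increased frequency of bowel movements or change in stool consistency".
- **Comparison (17.2.3).** "Categorical outcomes like any retreatment, any toxicity, radiologic response, pathologic response will be described by counts, percent", with a chi-square test between arms. "Quantitative outcomes like number of retreatments and number of toxicities" are compared by t-test. Neither measure has a grade or term definition.
- **Other capture.** The study calendars (Tables 2 to 4) have a Toxicity Notation row, and section 14.0 says that adverse events are captured throughout. Neither gives a grade or a list of terms.

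**The concern.** A reader who takes the floor in 10.3 at face value will read the any-toxicity result as covering all toxicity of grade 2 or higher. Under 12.3.1 it would not. A patient with grade 2 nausea counts; a patient whose only event is grade 2 skin irritation does not.

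The dividing line follows one arm's list more closely than the other's: every expected TACE symptom is collected at grade 2, but only part of the acute SBRT list is. Comparing toxicity is a stated secondary objective, and the background suggests that SBRT may be the less toxic treatment. An undefined composite with an uneven threshold is open to challenge whichever way the result falls.

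**Working it through.** **1. The plan's own figures.** With 98 patients per arm, the chance of at least one event is 1 − (1 − p)^98. This gives 1 − 0.95^98 = 99.3% and 1 − 0.97^98 = 94.9%, matching the 99% and 95% in 17.2.3. The widest 95% half-width is 1.96 × √(0.5 × 0.5 / 98) = 0.099, which agrees with "the 95% confidence intervals will have precision of 10% or tighter". None of these figures is in dispute. They describe only events that are collected: under 12.3.1 a grade 2 event outside the four symptoms is not recorded as an adverse event, whatever its true rate.

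**2. Collection set against the lists.**

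| Expected acute effect | TACE list (10.1) | SBRT list (10.2) | Grade 2 collected (12.3.1) |
|---|---|---|---|
| Abdominal pain / discomfort | yes | yes | yes, if discomfort is recorded as pain |
| Nausea | yes | yes | yes |
| Vomiting | yes | yes | yes |
| Fatigue | yes | yes | yes |
| Weight loss | no | yes | no |
| Anorexia | no | yes | no |
| Skin irritation | no | yes | no |
| Bowel change | no | yes | no |

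The long-term SBRT effects in 10.3 (rib fracture, myositis and biliary obstruction among them) are also collected only from grade 3.

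**3. What is missed.** Let m be the number of patients in an arm whose only events of grade 2 or higher are unlisted grade 2 events. The observed any-toxicity difference (SBRT minus TACE) equals the true difference minus (m_SBRT − m_TACE)/98, so each net patient shifts it by 1/98 = 1.02 percentage points. For number of toxicities the loss is wider, because every unlisted grade 2 event drops out, including those in patients already counted. The documents give neither m nor any grade 2 rate, so the shift has neither a derivable size nor a derivable sign.

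**4. Can a harmless size be named?** Assume equal true toxicity, 98 per arm, an uncorrected chi-square test and a two-sided 5% level (stated in 17.1, assumed here for toxicity). Hold the TACE count fixed and lower the SBRT count until p < 0.05, using χ² = (difference in proportions)² / [2p̄(1 − p̄)/98]. For 20 against 10 patients, p̄ = 30/196 = 0.153 and χ² = 0.01041/0.002646 = 3.93, so p = 0.047. The TACE counts are assumptions:

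| TACE count of 98 | Smallest significant gap | Points | p at that gap | p one patient short |
|---|---|---|---|---|
| 5 | 5 | 5.1 | 0.024 | 0.097 |
| 10 | 7 | 7.1 | 0.045 | 0.096 |
| 20 | 10 | 10.2 | 0.047 | 0.078 |
| 29 | 12 | 12.2 | 0.043 | 0.066 |
| 39 | 13 | 13.3 | 0.049 | 0.070 |
| 49 | 14 | 14.3 | 0.043 | 0.061 |

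A continuity correction adds one patient in each row from 10 to 49; at 5 of 98 no gap then reaches 5%. The answer depends on a rate that the documents do not give, so no general threshold can be stated below which the loss is harmless.

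**The case against.** The case against has real force on four points.

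- **There is no contradiction.** A reader might infer that 10.3 and 12.3.1 conflict. They do not: the floor in 10.3 removes grade 1, and everything collected under 12.3.1 passes it. Limited grade 2 collection, applied alike to both arms, is a legitimate choice. What remains is that the composite is undefined and its thresholds are not uniform.
- **The four symptoms are largely shared.** Fatigue, nausea and vomiting are on the SBRT list too, and abdominal discomfort is close to abdominal pain. This weakens any suggestion that the choice was one-sided. It does not bring in the other acute SBRT terms.
- **Other data cover part of the gap.** Weight is recorded at visits, and FACT-Hep asks about weight loss, bowel control, diarrhoea, appetite and bother from side effects; only skin irritation has no close counterpart. Laboratory values have their own comparison: "Lab measures will be described and groups compared as described using t-tests or Wilcoxon tests as appropriate". The Adverse events paragraph after 17.2.3 plans a breakdown by body system and severity, which separates grade 2 from grade 3. All this helps interpretation, but no text feeds weight, FACT-Hep or laboratory data into any toxicity, and the severity breakdown is limited by the same collection rule.
- **The text is ambiguous in two places.** The floor sits under a heading on long-term SBRT effects, although it is worded for the statistical analysis as a whole. The plan also uses toxicity and adverse event as separate words and does not say whether Toxicity Notation follows 12.3.1. The finding is therefore conditional on 12.3.1, the only explicit collection rule, governing both.

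**Conclusion.** The point holds as a minor one. If 12.3.1 governs what is counted, any toxicity and number of toxicities are mixed-threshold measures: four symptoms from grade 2, all other terms from grade 3. Because four acute SBRT effects fall on the uncollected side, the composite may be unbalanced between arms.

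A reader might go further and infer that the rule under-counts SBRT toxicity and so favours SBRT. The documents do not support that. They give no grade 2 rates for either arm, grade 2 TACE events outside the four symptoms are missed as well, and only the difference between arms in missed events matters. Nor do they support the opposite comfort, that a small net loss could not produce a significant result: the gap needed runs from 5 to 14 patients over the assumed TACE counts, and any net loss shifts the estimate.

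Only a secondary comparison is affected. The primary endpoint, the sample size and comparisons at grade 3 or higher stand.

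**What to change.** In 10.3 and 17.2.3, define the between-arm any-toxicity and number-of-toxicities comparisons as grade 3 or higher for all terms. Compare abdominal pain, nausea, vomiting and fatigue at grade 2 or higher as a separate endpoint. State that the Toxicity Notation rows follow 12.3.1.

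This costs wording only and uses data already collected. It makes the comparison uniform but does not recover the missing events: other grade 2 toxicity stays unmeasured in both arms, and the report should say so. It also adds one compared endpoint.

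The alternative is to collect all events of grade 2 or higher in both arms. That would close the gap but is not cheap. It adds every grade 2 event, abnormal laboratory findings included, for up to 24 months, with source documents due within a week of each visit and quarterly review of all adverse events (18.2). It is worth considering only if the sponsor accepts that burden.
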